## Abstract/Summary of the research

Professional musicians are exposed to chronic high volume of continuous and repeated physical movements, sometimes in challenging and ergonomically unfavourable anatomical body positions, in order to acquire and improve technical playing skills. As a consequence, musicians are vulnerable to developing adverse playing-related musculoskeletal disorders (PRMDs) that may affect the manner in which and the extent to which music can be practised and performed.

In order to find out effective solutions for PRMDs and to develop future preventive measures, it is fundamental to firstly identify the main risk factors that play a significant role in the development of adverse musculoskeletal (MSK) conditions and symptoms.

The aim of the study will be to identify those factors associated with increased risk of PRMDs among music students. A further goal is to characterise and describe the clinical features of PRMDs, as well as determine the evolving course of PRMD's in music students during their professional training.

All pre-college and university-level students from several European music academies will receive an invitation to complete a web-based questionnaire survey at each of three occasions (baseline; 6-months follow-up; 12-months follow-up).

The web-based survey will include questions about any pain, PRMD and/or MSK problem they may have due to their musical practice, and different outcome measures (i.e. lifestyle and physical activity, practice habits, behaviour toward prevention and health history, level of stress, perfectionism, fatigue and disability).

To the best of our knowledge, no other longitudinal studies on risk factors for PRMDs have been conducted so far. Therefore, the study can be considered as an opportunity to fill the gaps of current research on PRMDs and generate new knowledge in educational and employment musical contexts.

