# Background/Rationale of the project

It has been shown that professions with high physical demands and/or frequently repeated movements like computer use are associated with a higher prevalence of MSK problems (Roquelaure et al. 2006; Sim et al. 2006; Cote et al. 2008). Similarly, professional musicians are exposed to chronic high volume of continuous and repeated physical movements and are vulnerable to developing adverse MSK conditions and symptoms (Kok et al. 2013; Chan and Ackermann 2014), that may affect the manner in which and the extent to which music can be practised and performed (Kok et al. 2013; Chan and Ackermann 2014). Indeed, this phenomenon was described by Zaza et al. (1998) as playing-related musculoskeletal disorders (PRMDs) and includes "any pain, weakness, numbness, tingling, or other physical symptoms that affect a musicians' capacity to sing or to play their instruments at the level they are accustomed to". This definition does not include mild transient aches or pains. In fact, according to Zaza et al. (1998), musicians use the words mild, just, slightest, normal and little to describe such aches and pains that would not be considered to be related to PRMD, because they don't affect the ability to play the musical instrument and are considered as "normal" as every-day pain (Zaza et al. 1998).

Current literature suggests that PRMDs do not only occur when entering the professional world, but are already present at the very beginning of musicians' professional education. A study reported that 25% of music students at university level, admitted that they had suffered from PRMDs, before starting their degree course (Spahn et al. 2004). Other cross-sectional studies have indicated that 43% of university-level students of music experienced a health problem related with their activity as musicians during the early stages of their education (Zaza 1992). Brandfonbrener

(2009) reported a playing-related pain prevalence between 84% and 87% among first year music students at university level and found that the majority had already suffered from PRMDs as pre-college students or even younger. Moreover, it has been shown that at least 45% of university-level students of music seek help from clinical professionals during their training because of PRMDs (Spahn et al. 2004; Williamon and Thompson 2006).

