#### Research questions and hypotheses

Primary research question:

What are the main factors associated with increased risk of PRMDs in music students undertaking professional training?

Secondary research questions/objectives:

- 1. What is the prevalence of musculoskeletal disorders among university-level students in comparison with pre-college students?
- 2. Monitor and characterise the impact of the transition between pre-college and university-level music training on the development of PRMDs.
- 3. (Are there any differences in the severity and symptoms associated with PRMDs among music student groups at different levels of music training?)
- 4. Monitor and characterise the time course of PRMD development

- 5. (Are there significant differences in PRMD incidence between university-level students and pre-college students?
- 6. During training, do music students develop any type of musculoskeletal disorder that doesn't affect their ability to play at the level to which they are accustomed to?
- 7. Characterise health related quality of life and outcomes in music students at different stages of professional training.

Considering the aims and the research questions of the programme, the following hypotheses are formulated:

H1: The development of PRMDs is associated with a multitude of risk factors (i.e. age, gender, number of hours of practice, previous history of injury, poor physical status, psychological stress, perfectionism, fatigue) among music students.

H2: There is a higher prevalence of PRMDs among university-level students in comparison with precollege students.

H3: There is a higher prevalence of PRMDs among university-level students in the early stages of their training (transition between university-level and pre-college).

H4: University-level students develop more PRMDs over the years of their training than pre-college students.

H5: During their training, music students of both levels develop MSK disorders that affect their ability to play at the level they are accustomed to.

H6: Health and quality of life among music students is progressively poorer over the years of training (from the last two years of pre-college to the last years of Master-level)

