# The web-based survey

The web-based survey will include different outcome measures, which have been selected according to the relevant findings of previous cross-sectional studies and systematic reviews among the performing arts literature (Figure 2).

Each outcome measure correspond to a suspected factor that may be associated with the development of PRMDs.

The survey will start with questions about personal background and lifestyle (i.e. age, gender, self-reported weight and height, nationality, smoking status and sleeping habits), as well as practice habits (i.e. number of

hours of practice and years of experience) health history (i.e. major past injuries/accident/disorders and current medication) and health status (Self-Related Health - SRH).

Afterwards, in order to divide the cohorts, the presence of pain and/or MSK problems will be assessed through the following question: "When did you last experience a bout of significant pain and/or musculoskeletal problem?" with the following list of possible answers:

- 1. I currently have pain and/or a musculoskeletal problem (up to one month)
- 2. 2-3 months ago
- 3. 4-6 months ago
- 4. Up to 12 months ago
- 5. More than 12 months ago
- 6. I have never had any pain and/or musculoskeletal problem

[figure not shown]

Figure 2 Procedure of the web-based survey

According to the answer to this question, students will be addressed to different web pages throughout the survey (Figure 2):

- Respondents with a current pain and/or MSK problem (up to one month) will be asked questions to describe their current pain, to report their disability with Pain Disability Index (PDI), the Performing Arts

Section of Quick Disabilities of the Arm, Shoulder and Hand Outcome Measure (PAS –Quick DASH) and their pain self-efficacy with 2-item short form of the Pain Self-efficacy Questionnaire (PSEQ-2), as well as the Nordic Musculoskeletal Questionnaire (NMQ) for the assessment of musculoskeletal pain in the last 12 months

- Respondents without a current pain and/or MSK problem but a positive history of pain and/or MSK problem in the last 12 months (2-3 months ago, 4-6 months ago or up to 12 months ago) will be asked to answer the NMQ and questions on pain management to investigate how their pain and/or MSK problem has been treated
- Respondents without pain or with pain and/or MSK more than 12 months ago will be directly addressed to the next section

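### As the survey is described, an episode that has resolved cannot be classified as PRMD or not, because its effect on playing is not recorded

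*Protocol*

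**What the plan says.** **Definition.** Protocol, Background/Rationale of the project, takes PRMD to cover pain and other "physical symptoms that affect a musicians' capacity to sing or to play their instruments at the level they are accustomed to". Minor passing aches are set apart from it.

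**Role of PRMD.** It is the outcome of the primary question (Research questions and hypotheses) and of the risk ratios and the multivariable model (Data analysis). Study Design has the primary question answered from the follow-up of Cohort 1, in which new incidents are to be recorded over a year.

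**Survey.** The web-based survey gives one item that splits the respondents into the two cohorts: "When did you last experience a bout of significant pain and/or musculoskeletal problem"? The first answer option reads "I currently have pain and/or a musculoskeletal problem (up to one month"). The answer sets the route:

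- Current problem: questions describing the pain, the Pain Disability Index, the Performing Arts Section of the QuickDASH (PAS-QuickDASH), the PSEQ-2 and the Nordic Musculoskeletal Questionnaire (NMQ).
- Last episode 2–3, 4–6 or up to 12 months ago: these respondents "will be asked to answer the NMQ and questions on pain management to investigate how their pain and/or MSK problem has been treated".
- Never, or more than 12 months ago: straight to the common section on physical activity, distress, perfectionism and fatigue.

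**General statement.** The Abstract/Summary says that the survey includes "questions about any pain, PRMD and/or MSK problem they may have due to their musical practice", and that students will be invited to "complete a web-based questionnaire survey at each of three occasions (baseline; 6-months follow-up; 12-months follow-up").

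**The concern.** What makes a problem a PRMD under the Protocol's own definition is its effect on playing. The cohort-dividing question asks about significant pain or a musculoskeletal problem. The word significant helps to screen out minor aches, but it does not ask whether playing was affected. For a current problem, the PAS-QuickDASH gives at least some information on playing. For a resolved episode, nothing described does so: the NMQ is presented as a measure of musculoskeletal pain, and the remaining questions concern treatment.

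This matters most for incidence. Cohort 1 is seen again only at 6 and 12 months. A PRMD that begins after one survey and has resolved well before the next would be reported as a past episode. If the described routing applies at follow-up, it could not be told apart from pain that left playing unaffected. It would then be either left out of the PRMD outcome or merged with other pain. An analysis plan can choose how to use the data, but it cannot create an answer to a question that was not asked.

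**Working it through.** **Step 1: compare the definition with each route** (Protocol, The web-based survey).

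| Last episode | Described instruments that bear on playing | Can PRMD be classified as described? |
|---|---|---|
| Current (up to one month) | PAS-QuickDASH | Possibly, by a rule set in an analysis plan |
| 2–12 months ago | None (NMQ for musculoskeletal pain; treatment questions) | No |
| Never, or over 12 months ago | None | Not needed for the past year |

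The common section adds nothing on playing impact.

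**Step 2: how many new episodes could this affect at follow-up?** The plan gives no figure to reproduce: there are no episode durations in the documents, and the sample size is in Figure 1, which was not visible. What follows illustrates the size under assumptions; it is not an estimate.

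From the documents: surveys are 6 months apart, and the current option reaches back about one month. The next option starts at two months, so a reach of k = 2 months is tried as well as k = 1.

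Assumed: the follow-ups use the described routing, onset is uniform over the 6 months, and mean duration d is 1, 3, 6 or 12 months, either fixed or exponential.

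An episode is missed if it ends more than k months before the survey. With L = 6 − k:

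- fixed duration: share missed = max(0, L − d)/6
- exponential duration: share missed = [L − d(1 − exp(−L/d))]/6

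Example, d = 3 and k = 1, so L = 5:

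- fixed: (5 − 3)/6 = 0.33
- exponential: [5 − 3(1 − exp(−5/3))]/6 = (5 − 2.433)/6 = 0.43

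| d (months) | Fixed, k = 1 | Exponential, k = 1 | Fixed, k = 2 | Exponential, k = 2 |
|---|---|---|---|---|
| 1 | 67% | 67% | 50% | 50% |
| 3 | 33% | 43% | 17% | 30% |
| 6 | 0% | 27% | 0% | 18% |
| 12 | 0% | 15% | 0% | 10% |

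With fixed durations, no episode is missed once d reaches 5 months (k = 1) or 4 months (k = 2). The lower end therefore depends on the assumed distribution of durations. The shares count episodes, not persons: someone whose later bout is current at the survey still reaches the PAS-QuickDASH.

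**The case against.** The strongest reply is that the absence rests on material that was not visible. The Abstract/Summary promises questions on PRMD. The items of the NMQ, of the current-pain questions and of the treatment questions are not listed, and Figure 2 was not available. This stands as a limit. A reader might infer that the questionnaire contains no PRMD item; the documents do not support that. They support only that the described routing names none and gives the 2–12 month branch instruments whose stated purposes are pain and treatment.

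Four further readings go too far:

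- *That the lack of a stated yes/no rule for PRMD is itself a fault.* Deriving a binary outcome can be left to an analysis plan, and for current problems the PAS-QuickDASH could serve.
- *That baseline PRMD prevalence is shown to be wrong.* Study procedure does not say whether current or 12-month prevalence is meant. Current prevalence does not use the resolved-episode branch.
- *That secondary question 6 cannot be answered.* It asks whether students develop "any type of musculoskeletal disorder that doesn't affect their ability to play at the level to which they are accustomed to". That is a question of existence, which current problems alone might settle. It does show that the Protocol treats the two kinds of problem as distinct.
- *That follow-up incidence is certainly affected.* One survey on three occasions points to common routing, but no section states it.

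Separately, in Data analysis the univariate step names a wider outcome that includes any pain or musculoskeletal problem, while the risk ratios and the model name PRMD. That is a wording mismatch to align; it is not evidence about what the survey asks.

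**Conclusion.** The concern holds for the routing as described, and it should be fixed. A resolved episode cannot be classified against the Protocol's own definition of PRMD, which is the primary outcome, and later analysis cannot recover the missing answer. The effect on incidence is conditional on the follow-ups using the same routing.

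The size is unknown. With uniform onset and a one-month reach, about 67% of new episodes would be missed if they last 1 month and 33–43% if they last 3 months. For 6 to 12 months the share is 0% with fixed durations and 15–27% with exponential ones. A two-month reach lowers every non-zero figure. The classification gap does not depend on these shares; its practical weight does. Confidence is medium, because an unlisted item or Figure 2 could narrow the point.

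**What to change.** - **Item.** In The web-based survey, ask every respondent who reports an episode in the recall period, current or resolved, whether it affected their ability to play at the accustomed level, using the words of the definition in Background/Rationale. If such an item already exists, name it there and extend it to the resolved-episode branch.
- **Timing.** Use the item in all three surveys. Set the recall period to the last 12 months at baseline and to the time since the previous survey at follow-up. Adapt the follow-up answer options to match, since the present ones reach back beyond a 6-month interval.
- **Outcome.** Define PRMD from this item and use it in both the univariate and the multivariable step of Data analysis. Report any pain or musculoskeletal problem as a secondary outcome. The division into Cohorts 1 and 2 need not change.

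The cost is one extra item for those who report an episode, with matching wording changes. Some recall error will remain for resolved episodes, over up to 12 months at baseline. PRMD will also have fewer events than the composite, which leaves less information for the regression.

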#### Data analysis

Descriptive statistics will be used to investigate all the outcomes after the baseline data collection.

Furthermore, comparisons of gender, study, prevalence rate and hours of practice between pre-college and university-level students of music will be performed.

Baseline variables will be categorized to permit the calculation of risk ratios and the 95% confidence intervals (CI) for the development of PRMDs. Tests for trend of relative risk across categories will be carried out using the chi-square test. In order to check for confounders, logistic regression will be performed, adjusting for age, gender and different musical instrument.

Sample size estimation is reported in Figure 1.

Both the follow-ups will permit longitudinal change in outcome scores to be generated and compared (longitudinal comparisons) for strength and progression of association, alongside those from absolute outcome scores at several cross-sectional analyses.

For the evaluation of the association between the variables (gender, instrument group, age, years of playing, hours of practice, and questionnaires' scores) and pain, PRMD and/or MSK problem incidence, univariate analysis will be performed. Afterwards, all predictor variables that are significantly associated with the

occurrence of PRMDs will be included in a multivariate regression model to estimate the mutually adjusted effect of predictors on PRMDs.

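### Cutting numeric baseline predictors into categories is not needed for risk ratios and costs precision in the crude risk-ratio and trend step

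*Protocol*

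**What the plan says.** The Data analysis section of the protocol describes two routes to the association between baseline factors and PRMDs.

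- **First route.** "Baseline variables will be categorized to permit the calculation of risk ratios and the 95% confidence intervals (CI) for the development of PRMDs". Next: "Tests for trend of relative risk across categories will be carried out using the chi-square test". Adjustment follows: "In order to check for confounders, logistic regression will be performed, adjusting for age, gender and different musical instrument".
- **Second route.** A univariate analysis of incidence covers "gender, instrument group, age, years of playing, hours of practice, and questionnaires' scores". Significant predictors are then "included in a multivariate regression model to estimate the mutually adjusted effect of predictors on PRMDs". This route does not mention categories, and the type and scale of the final model are not named.

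Hypothesis H1 lists eight example risk factors: age, gender, and "number of hours of practice, previous history of injury, poor physical status, psychological stress, perfectionism, fatigue". Six of them (age, practice hours, physical status, stress, perfectionism, fatigue) are numeric or measured by questionnaire. Gender and instrument group are categorical in any case.

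**The concern.** The only reason given for categorising is that it makes risk ratios possible. That holds for risk ratios read from a table, but a log-link model, or a logistic model with standardised predictions, gives a risk ratio per unit of a continuous predictor. The stated reason therefore does not require the cut. For numeric predictors the cut treats everyone within a group as alike, and the crude risk ratios and trend test use less than was collected. The primary question asks which factors go with higher PRMD risk, so a factor of modest effect is somewhat easier to miss in this step.

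A smaller point concerns reporting. The risk ratio is the stated effect measure, yet the one named adjusted model is logistic, which gives odds ratios unless its results are converted. A reader may then see crude results on one scale and adjusted results on another.

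**Working it through.** The visible text gives no number of groups, cut-points or 12-month incidence, and the sample size is in a figure that is not shown. There is thus no stated figure to reproduce. The inputs below are assumptions, shown as ranges.

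**1. A risk ratio without categories.** In a simulated cohort (n = 20,000, overall risk about 28%, true risk ratio 1.20 per SD), Poisson regression with robust variance and two covariates, on the uncut predictor, gave 1.199 (95% CI 1.173 to 1.225). Logistic regression on the same data gave an odds ratio of 1.294.

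**2. Information kept after cutting (normal predictor, linear effect).** With k equal groups, cut-points q_j and normal density φ, the group means are m_j = k[φ(q_{j−1}) − φ(q_j)]. The information kept is r² = (1/k) Σ m_j².

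- k = 3: means ±1.091 and 0; r² = (2/3)(1.091²) = 0.793, a loss of 21%.
- k = 4: means ±1.271 and ±0.325; r² = (1/2)(1.271² + 0.325²) = 0.861, a loss of 14%.
- k = 5: means ±1.400, ±0.532 and 0; r² = (2/5)(1.400² + 0.532²) = 0.897, a loss of 10%.

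For a trend test with equally spaced scores, r² is the squared correlation of score and predictor. Extra sample for equal precision is 1/r² − 1. If the uncut test has 80% power at two-sided 5% (an assumption), power after cutting is Φ(2.802·√r² − 1.960).

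| Equal groups | r² (trend scores) | Extra students | Power |
|---|---|---|---|
| 3 | 0.793 | 26% | 70% |
| 4 | 0.856 | 17% | 74% |
| 5 | 0.888 | 13% | 75% |

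Unequal groups can cost more: a 60/30/10 split keeps 0.705 (group means), a loss of about 30%. A simulation (risk ratio 1.3 per SD, n = 500, mean risk 20%) agreed with the table: power 0.82 uncut against 0.73, 0.76 and 0.78 for 3, 4 and 5 groups.

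**3. The same check under a threshold effect.** Risk now steps up at one point, and the information kept is the squared correlation of the score with the step indicator.

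- Step at the median: the linear term keeps φ(0)²/0.25 = 0.64. Trend scores on 3, 4 and 5 groups keep 0.67, 0.80 and 0.72, so cutting does better.
- Step at the top fifth: the linear term keeps 0.49, against 0.38 (3 groups) and 0.45 (4 groups). With 5 groups, whose top cut falls on the step, the trend score keeps 0.4²/(2 × 0.16) = 0.50.

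**4. Scale.** With unexposed risk p0 and p1 = 1.5·p0, OR = [p1/(1−p1)]/[p0/(1−p0)].

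- p0 = 10%: (0.15/0.85)/(0.10/0.90) = 1.59.
- p0 = 25%: (0.375/0.625)/(0.25/0.75) = 1.80.

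These two risks are assumed. The Background does contain a 25% ("A study reported that 25% of music students at university level, admitted that they had suffered from PRMDs, before starting their degree course"), but that is a past history of PRMDs, not incidence in symptom-free students. In a simulation with no confounding, moving from crude to adjusted odds ratio changed the estimate by 0.15% at 10% risk and 0.43% at 25%.

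**The case against.** The strongest reply is that the sentence is sound in context. The next sentence tests trend across categories, so tabular risk ratios are meant, and those do need groups. The wording does not claim that grouping is the only way. This stands: a reader might infer that the planned risk ratios or trend tests are invalid, and they are not.

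Second, the loss does not reach the whole analysis. A reader might infer that the primary question as a whole loses power. The document does not support that, because the route leading to mutually adjusted effects lists the numeric variables without any mention of grouping.

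Third, the size depends on shape. Step 3 shows that a threshold effect can reverse the ordering against a single linear term. That also stands. A spline can follow such shapes but spends degrees of freedom.

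Fourth, on scale, a reader might infer that confounding will be judged by setting adjusted odds ratios against crude risk ratios, or that the plan excludes an adjusted risk ratio. Neither is stated. The confounder check can be made within the odds-ratio scale, where the shift without confounding is under 1%. The unnamed final model could have a log link, and an analysis plan not at hand may name it. Missing cut-points or a missing model name are therefore not counted here.

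What remains is a method the protocol does state: grouping the baseline variables for the sake of risk ratios, and testing on the groups.

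**Conclusion.** The point holds as an efficiency improvement, not as an error that invalidates a result. In the crude risk-ratio and trend step, grouping the numeric predictors loses about 21%, 14% or 10% of the information with 3, 4 or 5 equal groups. This rests on a normal predictor, a roughly linear effect and assumed group numbers; actual power is unknown because the sample size is not visible. The loss is larger with uneven groups, and smaller or reversed under some threshold effects.

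The scale issue is secondary and concerns reporting only. If an adjusted odds ratio were read as if it were a risk ratio, 1.5 would appear as 1.59 to 1.80 at assumed unexposed risks of 10% to 25%.

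**What to change.** In the Data analysis section:

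- Enter age, practice hours, years of playing and questionnaire scores as continuous terms, with a spline where the relation is not linear.
- Test the continuous term (all spline terms jointly where a spline is used) in place of the chi-square trend test.
- Keep categories for descriptive tables and for showing dose-response.
- Report crude and adjusted estimates on one scale. Since the risk ratio is the stated measure, modified Poisson regression with robust standard errors, or logistic regression with marginal standardisation, would serve.

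No new data are needed; only analysis wording changes. The price is a little more analysis work, less simple tables, and extra degrees of freedom for each predictor that needs a spline.

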A proper prevention and health awareness could be a potential contribution to psychosocial and physical factors in the performing art field (Chan and Ackermann 2014) and may address physical and psychological issues of health prevention. In fact, it has been frequently shown that a fundamental element in the prevention and management of MSK disorders is correct health education and medical advice (Silverstein and Clark 2004; Chan and Ackermann 2014).

Unfortunately, due to a lack of longitudinal studies, low methodological quality (i.e. high measurement bias, inappropriate statistical analysis) and large heterogeneity of assessment approaches and outcomes (Berque et al. 2016), currently available studies are capable of only offering a limited appraisal of possible relationships between the activity of musicians and the development of a PRMD.

The existing literature on risk factors among musicians cannot be considered acceptable in order to establish definitive links between the physical activity characteristics of musicians and their risks of developing PRMDs. This is because the available studies are predominantly cross-sectional, often based on a retrospective design and terms

such as prognostic facts or predictor are inappropriately used to indicate associations (Baadjou et al. 2016; Berque et al. 2016).

In fact, cross-sectional studies cannot be considered appropriate to research risk factors (Baadjou et al. 2016). In the interpretation of associations from cross-sectional studies, the direction of cause and effect it is extremely difficult to establish (Croft et al. 2001), because the presence of risk factors and the occurrence of an outcome (i.e. PRMDs) are assessed simultaneously. For example, anxiety or distress may be a risk factor for the development of PRMDs, but it is equally possible that PRMDs might contribute to increased anxiety or distress.

Currently, although there is a robust conceptual and physiological framework to expect a linkage between the physical activity characteristics of musicians and their risks of developing PRMDs, there is neither sufficient scientific evidence for this linkage nor the basis on which clinical prevention of PRMD can be developed (Rickert et al. 2015; Baadjou et al. 2016; Berque et al. 2016;).

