All respondents will be addressed to the next section, including the outcome measures:

International Physical Activity Questionnaire – short form (IPAQ-SF) for the assessment of physical status Kessler Psychological Distress Scale (K-10) for the assessment of anxiety and stress

Multidimensional Perfectionism Scale – short form (HFMPS-SF) for the assessment of perfectionism

The Chalder Fatigue Scale (CFQ-11) for the assessment of fatigue

Afterwards, all students (including those who will choose the sixth option) will be addressed to:

- International Physical Activity Questionnaire short form (IPAQ-SF) for the assessment of physical status
- Kessler Psychological Distress Scale (K-10) for the assessment of anxiety and stress
- Multidimensional Perfectionism Scale short form (HFMPS-SF) for the assessment of perfectionism
- The Chalder Fatigue Scale (CFQ-11) for the assessment of fatigue

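### The change-score and same-survey associations use scores recorded after onset, so for distress or fatigue they may show the effect of the PRMD; they need a time-order rule or a descriptive label.

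*Protocol*

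**What the plan says.** The primary question in the protocol's Research questions and hypotheses is "What are the main factors associated with increased risk of PRMDs in music students undertaking professional training". H1 lists psychological stress, perfectionism and fatigue among the candidate factors. The web-based survey section says of the instruments: "Each outcome measure correspond to a suspected factor that may be associated with the development of PRMDs". The K-10 (distress), HFMPS-SF (perfectionism), IPAQ-SF (physical activity) and CFQ-11 (fatigue) go to every respondent, after the question on when pain or a musculoskeletal problem last occurred. The Abstract says the survey is completed at baseline, 6 months and 12 months.

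The Data analysis section then sets out three strands:

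- **Baseline risk ratios.** "Baseline variables will be categorized to permit the calculation of risk ratios and the 95% confidence intervals (CI) for the development of PRMDs", followed by logistic regression adjusted for age, gender and instrument.
- **Change and repeated cross-sections.** "Both the follow-ups will permit longitudinal change in outcome scores to be generated and compared (longitudinal comparisons) for strength and progression of association", and this "alongside those from absolute outcome scores at several cross-sectional analyses".
- **Univariate screen and multivariable model.** Gender, instrument group, age, years of playing, hours of practice and questionnaire scores are related to incidence, and the significant ones go into a joint model. No survey is named as the source of the scores.

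The Background says that "cross-sectional studies cannot be considered appropriate to research risk factors" and gives distress as its example: "it is equally possible that PRMDs might contribute to increased anxiety or distress".

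**The concern.** A risk factor has to be measured before the event it is meant to explain. The second strand has no such limit. Its scores come from the same questionnaire that reports the problem, or from a difference that includes that questionnaire. If a PRMD makes a student more distressed or tired, both quantities will be associated with PRMD even when distress and fatigue play no part in causing it.

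Distress and fatigue are the candidate factors most open to this, and both are named in H1. The third strand selects variables by significance, so if follow-up scores were entered there, an association of this kind could pass into the final model.

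**Working it through.** **Time order of each planned comparison.** Take a Cohort 1 student whose problem begins at month 3.

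| Quantity related to this onset | Recorded at | Before onset? |
|---|---|---|
| Baseline score | month 0 | yes |
| 6-month score | month 6 | no |
| Change from 0 to 6 months | month 6 less month 0 | no |

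The pain question is retrospective: its answers include 2-3 and 4-6 months ago. A new problem reported at 6 months has thus begun before the scales in that survey are completed. In Cohort 2, and among current cases in the baseline cross-section, the problem is already present when the score is taken. One use of change is correctly ordered: change from 0 to 6 months against onset between 6 and 12 months, in students still free at 6 months. The protocol does not specify it.

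**Possible size.** The protocol gives no figure to reproduce here, and every input below is an assumption:

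- the score has no effect on onset, so the true odds ratio is 1.0;
- the score has SD 1 at each survey, with correlation 0.6 between surveys;
- having a PRMD raises the later score by d SD, with d from 0.3 to 0.5.

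With normal scores of equal variance in cases and non-cases, log OR per SD = d / σ, where σ is the SD of the quantity analysed.

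- Change score: σ = √(2 × (1 − 0.6)) = √0.8 = 0.894.
  - d = 0.3: 0.3 / 0.894 = 0.335, OR = 1.40.
  - d = 0.5: 0.5 / 0.894 = 0.559, OR = 1.75.
- Same-survey score: σ = 1.
  - d = 0.3: OR = exp(0.3) = 1.35.
  - d = 0.5: OR = exp(0.5) = 1.65.

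**Check by simulation.** The same model was simulated with 400,000 students per setting and incidence of 10%, 20% and 40%. Ranges are over the three incidences. The SD here is that of the whole sample, so values differ slightly from the formula.

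| PRMD-caused rise (SD) | Baseline score, OR per SD | Change score, OR per SD | Same-survey score, OR per SD |
|---|---|---|---|
| 0 | 1.00 | 1.00 | 1.00 |
| 0.2 | 1.00 | 1.25 | 1.22-1.23 |
| 0.5 | 0.99-1.00 | 1.76-1.79 | 1.66-1.67 |
| 0.8 | 0.99-1.00 | 2.52-2.67 | 2.26-2.37 |

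The next table gives the share of 1,000 simulated studies with p < 0.05 (two-sided t-test), for an assumed 300 students and 20% incidence.

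| PRMD-caused rise (SD) | Baseline score | Change score | Same-survey score |
|---|---|---|---|
| 0.2 | 5.3% | 34.4% | 25.0% |
| 0.5 | 5.3% | 97.0% | 93.3% |

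Scores taken before onset keep the nominal 5%. Scores taken after onset do not.

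**The case against.** The strongest reply is that the sentence on change scores is loose and may serve description only. It says the follow-ups permit comparison for strength and progression of association, without saying association with what. Several stated aims are descriptive: the time course of PRMDs, quality of life at different stages, H6 on worsening health, and the follow-up of Cohort 2. Measurement after onset is intended for those. The instruments also include the PDI, PAS-QuickDASH and PSEQ-2, given only to students with current pain, so not every outcome score can be a predictor of onset. Finally, which survey supplies a covariate is a detail often left to a SAP.

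Much of this stands. A reader might infer that the protocol will present change-score associations as evidence on risk factors, or that the advantage of the prospective design is lost for distress and fatigue. The documents support neither. The protocol does not say these associations will be called risk factors. The Study Design section assigns the primary question to the follow-up of Cohort 1, and the baseline risk ratios have the right time order there. The univariate screen is silent on the survey used, which is not the same as being wrong.

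What does not fall away is that the protocol affirmatively plans the second strand, calls its measures suspected factors, and nowhere marks these associations as descriptive or requires the score to precede onset. This is stated content that conflicts with the reasoning in its own Background, not merely detail deferred to a SAP.

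**Conclusion.** The point holds within limits. The exposure is confined to the change-score and repeated cross-sectional associations, and extends to the univariate and multivariable models only if follow-up scores enter them. The baseline risk ratios in Cohort 1 keep the prospective advantage.

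If a PRMD raises distress or fatigue, the exposed associations are biased away from no effect. The size is not known. The odds ratios of about 1.35 to 1.75 are illustrative and rest on the assumed rise, correlation and absence of a true effect; with rises from 0.2 to 0.8 SD they run from about 1.2 to 2.7. With no rise there is no bias. It is worth correcting because the remedy is cheap and the protocol already recognises the problem.

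**What to change.** Add to the Data analysis section:

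- Inference on risk factors, including the univariate and multivariable models, uses scores from the survey before the interval in which the problem arose, in students free of the problem at that survey.
- For onsets between 0 and 6 months, use baseline scores.
- For onsets between 6 and 12 months, use 6-month scores, or change from 0 to 6 months, in students still free at 6 months.
- Associations with scores from the same survey, or with change over the interval that contains the onset, are descriptive and are not evidence on risk factors.

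This needs no new data and no change to the surveys. The cost is that change scores can be related only to onsets between 6 and 12 months, so fewer events support that analysis.
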